7.3.2 Puffing/ Inhalation behavior question

At Day 1 and Day 30, during the use of P3P for PK assessment the site staff will be asked to observe the puffing/inhalation behaviour of the subjects and answer a question related to it. The staff will evaluate if the subject is using P3P by:

- puffing and holding the aerosol in the mouth for a short time and then inhaling (i.e. like a cigarette);
- puffing and immediately inhaling (without holding the aerosol in the mouth); or
- puffing and immediately exhaling, without inhalation;

At Day 2, V3, V4, V5, Day 29, the subjects will also answer the same question about their own puffing/inhalation behaviour.

Reported values at Day 1 will be considered as baseline values for the site staff assessment while reported values at Day 2 will be considered as baseline values for the subject assessment.

7.3.3 Nicotine/tobacco product use

Subjects will enter the number of P3P consumables used per day, the number of cigarettes used per day, or/and other tobacco and nicotine containing products used per day in a product use diary from Day 1 until the Discharge at V6 (including during the visits). For subjects who decide to quit using all tobacco and nicotine containing products the product use will no longer be captured. See section 7.9 for the definition of product exposure periods.

Average P3P consumables used per day during a period = Total number of P3P consumables used during the period/ duration of the period.

Similar definition will be made for:

- Average Cigarettes smoked per day during a period
- Average Heat not burn and/or smokeless tobacco products used per day during a period
- Average Other tobacco products (pipe, cigar, cigarillos, chewable...) used per day during a period
- Average occasions Electronic Cigarette used per day during a period

Also, the percentage of subjects having used any Nicotine Replacement Therapies over the period will be provided.

Change from baseline in average number of cigarettes used per day = Average number of cigarettes used per day reported at Screening - Average number of cigarettes used per day per period.

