7 DERIVED AND COMPUTED VARIABLES

Each individual change from baseline will be calculated by subtracting the individual subject's baseline value from the value at the timepoint.

Baseline definition by endpoint can be found in the different sections defining the derivation of each endpoint below and in section 12.1.4.

The geometric coefficient of variation (CV) for descriptive statistics will be calculated using the following formula:

$$CV = 100\sqrt{e^{\text{var}} - 1}$$

where var = the variance from the log transformed data.

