**Table 7: Categorical Variables Definitions Other Than Reported in eCRF**

Variable	Categories
Demographics	
BMI (kg/m ²)	Underweight: < 18.5 Normal range: ≥ 18.5 and < 25.0 Overweight: ≥ 25.0 and < 30.0 Obese: ≥ 30.0
Product Exposure Categories	≤ 5 P3P-1mg /Day $>5-10$ P3P-1mg /Day >10 P3P-1mg /Day ≤ 5 P3P-2mg /Day $>5-10$ P3P-2mg /Day >10 P3P-2mg /Day
Product Exposure Periods	
Detailed Product Exposure Periods	Product test Day 1 Day 2 Period 1 ([D3 –V3]) Period 2 ((V3-V4]) Period 3 ((V4-V5]) Period 4 ((V5-V6])
Overall exposure period	Day 1 to Day 29 inclusive

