12.1.7 Definitions of Product Exposure Categories

Product exposure categories will be created by calculating the average P3P consumption over the exposure period (from Day 1 to Day 29) as the total number of P3P consumables used during the exposure period / duration of the exposure period.

Subjects will be categorized according to their average P3P consumption in one of the 3 product exposure categories by variant (total of 6 subgroups):

- ≤ 5 P3P/Day

- >5-10 P3P/Day
- >10 P3P/Day

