12.5.4 Nicotine/Tobacco product use

The following variables:

- Average Cigarettes smoked per day during a period
- Change from baseline in average number of cigarettes used per day during a period

- Average Heat not burn and/or smokeless tobacco products used per day during a period
- Average Other tobacco products (pipe, cigar, cigarillos, chewable...) used per day during a period
- Average occasions Electronic Cigarette used per day during a period
- Percentage (%) of P3P used during a period with % P3P = $100 * \text{number of P3P} / (\text{number of P3P and CC})$
- Percentage of subjects having used any Nicotine Replacement Therapies during a period

will be summarized in a descriptive manner for each period being the time interval between 2 consecutive visits and also for the complete exposure period.

The data will be presented in the below outputs:

TFL number	Title
TABLES	
15.2.18.1	Descriptive Statistics of Average Cigarettes smoked /day - By Period – Safety Population
15.2.18.2	Descriptive Statistics of Average Cigarettes smoked /day By Product Exposure Category (≤ 5 P3P/day, $> 5 - 10$ P3P/day, > 10 P3P/day) - By Period – Safety Population
15.2.18.3	Descriptive Statistics of Change from Baseline in Average Cigarettes smoked /day - By Period – Safety Population
15.2.18.4	Descriptive Statistics of Average Heat not burn and/or smokeless tobacco products used /day - By Period – Safety Population
15.2.18.5	Descriptive Statistics of Average Other tobacco products (pipe, cigar, cigarillos, chewable...) used/day - By Period – Safety Population
15.2.18.6	Descriptive Statistics of Average occasions Electronic Cigarette used /day - By Period – Safety Population
15.2.18.7	Descriptive Statistics of Percentage (%) of P3P use - By Period – Safety Population
15.2.18.8	Percentage of subjects having used any Nicotine Replacement Therapies – By Period
LISTINGS	
15.1.18.1	Listing of Nicotine/Tobacco product use - By Period

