13.2 Topline Results

Topline results, composed of key statistics and study results listings, will be made available to PMPSA following database lock and prior to completion of the complete set of TFLs. The following tables, figures, and listings will be made available following database lock:

TFL no.	Title
TABLES	
15.2.4.1	Summary of Demographics and Other Baseline Characteristics – Safety Population
15.2.8.3	Descriptive Statistics of Product Exposure by Period - Safety Population
15.2.9.1	Descriptive Statistics of Background-Corrected and Uncorrected Pharmacokinetic Parameters of Nicotine (AUC _(0-4h) and C _{max}) at Day 1 and Day 30 – PK Population
15.2.9.2	Analysis of Background-Corrected and Uncorrected Pharmacokinetic Parameters of Nicotine (AUC _(0-4h) and C _{max}) at Day 30 and at Day 30 relative to Day 1 – PK Population
15.2.12.1	Descriptive Statistics of Background-Corrected Plasma Nicotine Concentration at Day 1 and Day 30 by Timepoint– PK Population
15.2.12.2	Descriptive Statistics of Uncorrected Plasma Nicotine Concentration at Day 1 and Day 30 by Timepoint– PK Population
15.2.13.2	Analysis of AUC _{VAS Craving (0-4h)} at Day 1 and Day 30 and Change from Day 1 at Day 30 – Randomized Population
15.2.18.3	Descriptive Statistics of Change from Baseline in Average Cigarettes smoked /day - By Period– Safety Population
15.2.23.1	Summary of Adverse Events – Safety Population
15.2.23.2	Summary of Adverse Events by System Organ Class and Preferred Term – Safety Population
15.2.25.1	Summary of P3P Product events by Subject - Safety Population
15.2.26.2	Summary of Clinical Chemistry Parameters - Safety Population
15.2.26.7	Summary of Hematology Parameters - Safety Population
15.2.26.12	Summary of Urinalysis Parameters - Safety Population
15.2.30.1	Descriptive Statistics of Spirometry Results- Safety Population
FIGURES	
15.3.2.1	Background-Corrected Plasma Nicotine Concentration-Time Profiles at Day 1 and Day 30- Linear-- PK Population
15.3.2.2	Uncorrected Plasma Nicotine Concentration-Time Profiles at Day 1 and Day 30–Linear- PK Population
15.3.3.1	VAS Craving Score Profiles By Timepoint at Day 1 and Day 30 – Randomized Population
LISTINGS	
15.1.23.1	Listing of Exposure Emergent Adverse Events
15.1.23.4	Listing of AEs leading to study discontinuation

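### SAP 7.3.3 reverses the sign of change from baseline in cigarettes per day against SAP section 7; secondarily, the per-day averages have no rule for unreported or post-discontinuation days

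*SAP*

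**What the plan says.** **Sign.** SAP section 7 sets one general rule: "Each individual change from baseline will be calculated by subtracting the individual subject's baseline value from the value at the timepoint". Section 7.3.3 then defines the cigarette variable, under the same label, as "Average number of cigarettes used per day reported at Screening - Average number of cigarettes used per day per period". Section 12.5.4 lists it as "Change from baseline in average number of cigarettes used per day during a period", and section 13.2 includes it in the topline set as "Descriptive Statistics of Change from Baseline in Average Cigarettes smoked /day - By Period" (Table 15.2.18.3, Safety population). The protocol endpoint (3.2, objective 3) asks for a comparison with Screening and fixes no direction. SAP section 9 does not mention the reversal.

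**Averages.** SAP 7.3.3 gives "Average P3P consumables used per day during a period = Total number of P3P consumables used during the period/ duration of the period", and cigarettes and most other products follow the same pattern. Section 12.5.4 summarises these "for each period being the time interval between 2 consecutive visits and also for the complete exposure period". Table 7 sets the overall period as "Day 1 to Day 29 inclusive". Section 12.1.7 forms the three product exposure categories (cut at 5 and 10 P3P a day) from average P3P consumption, taken "as the total number of P3P consumables used during the exposure period / duration of the exposure period".

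**Nearby rules.** SAP 7.3.3 and protocol 7.8.1 stop recording use once a subject quits all products. Protocol 12.1.4 says missing data are in general not imputed. SAP Table 9 makes it a major deviation if under 75% of diary reports are available over a period, or if there is a gap of more than 7 consecutive days. None of these defines the numerator or denominator of the average.

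**The concern.** The two subtraction orders cannot both apply to a variable called change from baseline, and 7.3.3 does not announce an exception. Where the SAP intends a before-minus-after quantity elsewhere (product weighing, 7.7), it calls it a weight difference and states the direction. Here a reader who takes the topline title at its word would read a positive value as more smoking. A programmer working from section 7 and one working from 7.3.3 would produce opposite signs.

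The denominator is a gap, not a contradiction. If a programmer sums the entries that exist and divides by calendar duration, a day without an entry lowers the average exactly as a day of no use would. If product was in fact used on that day, average use is understated, cigarette reduction is overstated, and a subject may fall into a lower exposure category. That category defines the stratified descriptive tables (12.1.1) and is a factor in the within-group Product Experience model (12.5.2.3). The percentage-of-P3P variable in 12.5.4 is a ratio of counts, so period duration does not enter it.

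**Working it through.** The documents report no numerical result for either definition, so there is no plan figure to reproduce.

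**1. Sign.** Let B be the Screening value and P the period average.
- Section 7: change = P − B. Section 7.3.3: change = B − P = −(P − B).
- B = 10, P = 4: section 7 gives −6; 7.3.3 gives +6.
- B = 10, P = 12: section 7 gives +2; 7.3.3 gives −2.
- The absolute value, SD and confidence-interval width are the same under both.

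**2. How many unreported days 75% completeness allows.** Detailed periods from Table 7, at nominal visit days:

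| Period | Days | Most unreported at ≥75% |
|---|---|---|
| Day 1 | 1 | 0 |
| Day 2 | 1 | 0 |
| Day 3–7 | 5 | 1 (4/5 = 80%) |
| Day 8–15 | 8 | 2 (6/8 = 75%) |
| Day 16–22 | 7 | 1 (6/7 = 85.7%) |
| Day 23–29 | 7 | 1 (6/7 = 85.7%) |
| Total | 29 | 5 |

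**3. Effect over the 29-day period with 5 unreported days.** This assumes unchanged use on those days and division of the available total by 29.
- 12 P3P a day: 12 × 24/29 = 9.93, so the subject moves from >10 to >5–10.
- Cigarettes, Screening 10, true average 4: recorded average 4 × 24/29 = 3.31. The reduction reads 10 − 3.31 = 6.69 against a true 6.00, an excess of 0.69 (11.5%).
- Who changes category: true averages above 10 up to 10 × 29/24 = 12.08, and above 5 up to 5 × 29/24 = 6.04. At 8 a day (8 × 24/29 = 6.62) and 14 a day (14 × 24/29 = 11.59) the category is unchanged.

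**4. Discontinuation after Day 15, overall period only, fixed 29 days.**
- 12 P3P a day: 12 × 15/29 = 6.21, against 12.00 over days on study.
- 4 cigarettes a day: 4 × 15/29 = 2.07, so the reduction reads 10 − 2.07 = 7.93 instead of 6.00.

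**5. Documented quit after Day 15.** Counting later days as zero gives 6.21 P3P and 2.07 cigarettes a day. Stopping the denominator at the quit gives 12.00 and 4.00. These answer different questions, so the convention has to be stated.

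**6. Short periods.** V3 may fall on Day 5 (window ±2 days), which leaves Days 3–5, three days. One missed entry gives 2/3 = 66.7%, below 75%.

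**The case against.** On the sign: 7.3.3 writes its formula out in full, so a programmer following it has one unambiguous instruction, and the tables are descriptive with no claim attached (12.1.6). That limits the harm to presentation. It does not remove the clash with section 7 or the misleading table title.

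On the denominator, the other side has several good points.
- A reader might infer that the SAP counts unreported days as zero. It does not say so. The formula needs total use, which is unknown if a day is unknown, and a silent zero is a form of imputation that protocol 12.1.4 in general rules out. The supportable statement is that the rule is missing.
- A reader might also take 7 unreported days as tolerable, since 22/29 = 75.9%. At nominal visit days that many must breach 75% in at least one detailed period, which is a major deviation if Table 9 is applied by period. Five is the defensible figure.
- Post-discontinuation zeros need not run through every period. Later periods are bounded by visits the subject does not attend and may not exist for that subject. The effect concerns the overall period.
- Sparse diaries are not ignored. SAP 11.1 allows subjects with major deviations to be considered for exclusion from any analysis population, although the Safety population definition (10.2) contains no such exclusion and Table 9 is not an averaging rule.
- Diary checks (protocol 7.8.1), data queries (11.2.1), on-site dispensing logs and return of used and unused product (6.5.1) should limit missing P3P counts. Product return gives no information on cigarettes.

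**Conclusion.** The sign definition is wrong as written. It reverses direction for every subject and period in a topline table and leaves size and precision unchanged. This rests only on the two SAP texts.

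The denominator point is secondary: an unstated rule with a conditional consequence. If calendar duration is used and use continued on unreported days, 5 such days shift a 6.00 reduction to 6.69 and move only those within the narrow bands above a cut-point into a lower category. If nothing was used on those days there is no error. The documents give no expected missingness, so the likely size in this trial cannot be stated, and they do not support a claim that product use will in fact be understated.

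**What to change.** 1. In SAP 7.3.3, define the change as period average minus Screening value. Alternatively keep the formula and rename the variable and Table 15.2.18.3 as reduction from Screening, with matching wording in 12.5.4 and 13.2. SAP section 3 already allows table titles to change without an amendment.
2. In 7.3.3 and 12.1.7, divide by the number of days in the period with a diary entry, up to discontinuation. State a minimum number of reported days per period, chosen so that it also works for the short ones; a flat 75% would blank a three-day Day 3–V3 period after one missed entry.
3. For documented quitters, state one convention, for example zero use after the quit date on the assumption of no relapse. The rule should not depend on use being reported later, because diary capture stops at the quit.

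The cost is SAP wording and code; no data collection changes. The downsides are that dividing by reported days assumes unreported days resemble reported ones, that some short subject-periods become missing, and that the quit convention would miss an unrecorded relapse.

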7.4 Nicotine Equivalents, CEMA, and Total NNAL

7.4.1 Values outside limits of quantification

Values below the lower limit of quantification (BLOQ) will be imputed using 0.5 x lower limit of quantification. For values above the upper limit of quantification (ULOQ), i.e., preceded by a “>”, for example “>xx,” the numerical xx will be used for calculation and reporting in summary tables.

7.4.2 Nicotine Equivalents in Urine

- Nicotine equivalents (NEQ = molar sum of free nicotine, nicotine-glucuronide, free cotinine, cotinine-glucuronide, free trans-3'-hydroxycotinine, trans-3'-hydroxycotinine-glucuronide) will be adjusted for creatinine in spot urine.

$$\text{NEQ [mg]} = (\text{free nicotine}_c [\mu\text{mol/L}] + \text{nicotine-glucuronide}_c [\mu\text{mol/L}] + \text{free cotinine}_c [\mu\text{mol/L}] + \text{cotinine-glucuronide}_c [\mu\text{mol/L}] + \text{free trans-3'-hydroxycotinine}_c [\mu\text{mol/L}] + \text{trans-3'-hydroxycotinine-glucuronide}_c [\mu\text{mol/L}]) * 162.2 [\mu\text{g}/\mu\text{mol}] * \text{urine volume [L]} / 1000 [\mu\text{g}/\text{mg}]$$

N.B. All concentrations must be in $\mu\text{mol/L}$ before applying the above formula.

The conversion factors will be applied as follows:

Free nicotine	The molecular weight is 162.232 g/mol. Therefore to convert nicotine from ng/mL to nmol/L, the result in ng/mL is multiplied by 6.164.
Nicotine glucuronide	The molecular weight is 338.356 g/mol. Therefore to convert nicotine from ng/mL to nmol/L, the result in ng/mL is multiplied by 2.955.
Cotinine	The molecular weight is 176.218 g/mol. Therefore to transform cotinine from ng/mL to nmol/L, the result in ng/mL will be multiplied by 5.675.
Cotinine-glucuronide	The molecular weight is 352.341 g/mol. Therefore to transform cotinine from ng/mL to nmol/L, the result in ng/mL will be multiplied by 2.838.
Trans-3'hydroxycotinine	The molecular weight is 192.217 g/mol. Therefore to transform trans-3' hydroxycotinine from ng/mL to nmol/L, the result in ng/mL is multiplied by 5.202.
Trans-3'hydroxycotinine-glucuronide	The molecular weight is 368.34 g/mol. Therefore to transform trans-3' hydroxycotinine from ng/mL to nmol/L, the result in ng/mL is multiplied by 2.715.

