In addition to the nicotine PK assessment in plasma, exposure to nicotine during the ambulatory exposure period will be assessed by measuring urinary concentrations of nicotine equivalents (NEQ) in spot urine adjusted for creatinine. During cigarette smoking, on average 98% of the nicotine dose can be accounted for in the urine. NEQ, which is the molar sum of nicotine and five of its phase I and phase II metabolites in urine, represents more than 90% of the total dose recovered in urine (29).

Biomarkers of exposure to HPHCs found in tobacco and cigarette smoke will be measured during the study to detect reduction in the levels of these BoExp. Changes in levels of the tobacco-specific BoExp, total NNAL (30), and the BoExp to acrylonitrile, CEMA (31) which are predominantly formed during combustion of tobacco will be measured in spot urine adjusted for creatinine. Adjustment for creatinine will be performed to normalize for volume of urine excretion. As P3P is a nicotine containing product and the aerosol generated by P3P does not generate by design HPHCs other than nicotine, the levels of CEMA and total NNAL may be further used to detect cigarette use in addition to P3P use during the ambulatory exposure period and used as a chemical verification of the self-reporting.

The activity of CYP2A6 will be measured. CYP2A6 activity drives the metabolism of nicotine to cotinine and subsequent metabolites. Nicotine metabolism by CYP2A6 varies between

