#### 7.4.1.2 Nicotine Equivalents in Urine

Nicotine Equivalents (NEQ): molar sum of nicotine, cotinine, trans-3'-hydroxycotinine, nicotine-N-glucuronide, cotinine-N-glucuronide and trans-3'-hydroxycotinine-O-glucuronide will be measured in spot urine at Admission (Day -1; V2), and V3-V6. The results will be normalized to urine creatinine and expressed as concentration adjusted for creatinine.

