### 7.6.2 Spot Urine Samples

Spot urine samples will be used for the urine drug screen, urine cotinine screen, urine pregnancy test, safety urinalysis, BoExp (NEQ, Total NNAL and CEMA) and creatinine analysis and for biobanking samples.

Spot urine for BoExp will be collected from V2-V6. Baseline values of BoExp will be assessed at V2 (Day -1) when spot urine should be collected prior to product test. At V6 (Day 29) spot urine should be collected before the start of the wash-out period.

Spot urine for biobanking will be collected at V2 (Day 1) and V6 (Day 30).

For spot urine collected for BoExp and biobanking, the time of collection as well as the total volume collected should be recorded.

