7.4.3 Concentrations adjusted for creatinine

Concentrations adjusted for creatinine in spot urine collection will be calculated as:

$$\text{Biomarker (adjusted for creatinine)} = \frac{[\text{Biomarker}]}{[\text{Creatinine}]}$$

where the [] indicated concentrations measured from the same spot urine collection.

This applies to NEQ, CEMA and total NNAL.

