12.5.5 Biomarkers of Exposure in Urine

Urinary concentrations adjusted for creatinine of biomarkers of exposure : Nicotine Equivalents (NEQ), total NNAL and CEMA will be considered log-normally distributed and summarized as described in section 12.1.3. The number and percent of values below LLOQ or above ULOQ will be presented in each summary table.

For each timepoint (Day 7, Day 15, Day 22, Day 29), the values and percent changes from baseline (Day -1) in the concentration adjusted for creatinine of NEQ, total NNAL and CEMA will be summarized by P3P variant, and by product use category.

The data will be presented in the below outputs:

TFL number	Title
TABLES	
15.2.19.1	Descriptive Statistics for Biomarkers of Exposure in Urine and Percent change from baseline - By Timepoint– Randomized Population
15.2.19.2	Descriptive Statistics for Biomarkers of Exposure in Urine and Percent Change from Baseline - By Timepoint – By Product Exposure Category - Randomized Population
15.2.19.3	Descriptive Statistics for Biomarkers of Exposure in Urine and Percent Change from Baseline - By Timepoint – By Sex - Randomized Population
LISTINGS	
15.1.19.1	Listing of Biomarkers of Exposure in Urine – By Timepoint - Results

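### The NEQ formula in SAP 7.4.2 multiplies by urine volume and returns milligrams, but the endpoint is a creatinine-adjusted concentration

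*SAP*

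**What the plan says.** SAP 7.4.2 opens by defining NEQ as a molar sum of nicotine and five metabolites that "will be adjusted for creatinine in spot urine". The formula displayed directly below is labelled as milligrams. It adds the six analyte concentrations in µmol/L, multiplies by 162.2 µg/µmol and by "urine volume [L"], and divides by 1000. It has no creatinine term.

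Every other statement of the variable asks for a concentration:

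- SAP 7.4.3 defines the adjusted biomarker as biomarker over creatinine, where the square brackets "indicated concentrations measured from the same spot urine collection", and lists NEQ among the biomarkers covered.
- SAP 12.5.5 names the analysis variables as "Urinary concentrations adjusted for creatinine of biomarkers of exposure" and summarises percent change from Day -1 at Days 7, 15, 22 and 29.
- Protocol 7.4.1.2, on NEQ: "The results will be normalized to urine creatinine and expressed as concentration adjusted for creatinine".
- Protocol 4.2: "Adjustment for creatinine will be performed to normalize for volume of urine excretion".

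For these samples protocol 7.6.2 says that "the time of collection as well as the total volume collected should be recorded". SAP section 9, which lists changes from the protocol analysis, mentions no change to NEQ.

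**The concern.** The formula that builds NEQ from its six components yields the amount in one urine collection, not a concentration. A programmer who codes 7.4.2 as displayed and then applies 7.4.3 divides milligrams by a creatinine concentration. Because volume is recorded, the program runs without error. The result scales with how much urine the subject passed, which is the dependence the creatinine adjustment is meant to remove.

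NEQ is the urinary measure of nicotine exposure during the ambulatory period (protocol 4.2). Its Day 29 to Day -1 ratio would be multiplied by the ratio of two sample volumes. The SAP names no reporting unit for adjusted NEQ, so a reader of the tables could not easily tell which version had been run.

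**Working it through.** **1. Unit of the displayed formula.** µmol/L × µg/µmol × L ÷ (µg/mg) = mg. This reproduces the unit printed in SAP 7.4.2, so the volume term is part of a complete formula and not a stray label.

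**2. Unit after SAP 7.4.3.** With the displayed result as numerator, mg ÷ (mg/L) = L. With the volume term removed, (mg/L) ÷ (g/L) = mg/g creatinine, which is the kind of quantity the protocol describes.

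**3. Same urine composition, different volume.** Illustrative inputs, not given in the documents: molar sum 50 µmol/L and creatinine 1 g/L at both visits, 150 mL on Day -1 and 300 mL on Day 29.

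- As displayed: 50 × 162.2 × 0.150 / 1000 = 1.22 mg, and 50 × 162.2 × 0.300 / 1000 = 2.43 mg. Dividing both by the same creatinine leaves a ratio of 2.00, reported as +100%.
- Without volume: 50 × 162.2 / 1000 = 8.11 mg/L, that is 8.11 mg/g creatinine at both visits. The ratio is 1.00.

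The ratio depends only on the two volumes, not on the assumed molar sum or creatinine.

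**4. Same excretion, diluted twofold.** Volume goes from 0.1 to 0.2 L, the molar sum from 50 to 25 µmol/L and creatinine from 1.0 to 0.5 g/L. The displayed formula gives 0.811 mg both times. Divided by creatinine concentration this is 0.811 and then 1.622, a spurious doubling. The concentration ratio is 8.11 mg/g both times.

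**5. Size at group level.** The documents give no volume data. Assume an SD of ln(volume) of 0.3, 0.5 or 0.7, independent volumes at the two visits and no systematic shift. The 95% range of the spurious factor on the Day 29/Day -1 geometric mean ratio is exp(±1.96 × √2 × SD / √n).

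| n | SD 0.3 | SD 0.5 | SD 0.7 |
|---|---|---|---|
| 1 (one subject) | 0.44–2.30 | 0.25–4.00 | 0.14–6.96 |
| 30 (one arm) | 0.86–1.16 | 0.78–1.29 | 0.70–1.43 |
| 12 (smallest sex subgroup) | 0.79–1.27 | 0.67–1.49 | 0.57–1.75 |

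The subgroup size is 40% × 30 = 12, the minimum share of each sex per arm (protocol 6.3), and applies to the planned by-sex table 15.2.19.3. A systematic volume difference between visits would pass in full into the geometric mean ratio at any n.

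**6. Conversion factors.** The six ng/mL to nmol/L factors in SAP 7.4.2 agree with 1000 / molecular weight to three decimals, so the problem is confined to the volume term.

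**The case against.** The best reply is that SAP 7.4.3 already states the correct rule. It requires a ratio of concentrations and says that this covers NEQ, and SAP 12.5.5 names the right analysis variable. No sentence says that the mg result is to be the numerator, so harm needs a programmer to put an amount where a concentration is called for. The mg figure could be a leftover intermediate. A programmer who divided it by the creatinine amount in the same collection would see volume cancel and would obtain the correct mg/g.

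The volumes and SDs are also assumed. Without a systematic shift the arm-level effect is added noise, not bias. NEQ is a descriptive secondary endpoint, SAP 12.1.6 makes no claim from individual intervals, and the biomarkers named for detecting cigarette use are total NNAL and CEMA.

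All of this stands as a limit on the weight of the point. It does not remove the conflict. SAP 7.4.3 takes NEQ as an input, and the only displayed formula that builds NEQ from its analytes is the one with the volume term. The step of dividing by creatinine amount is not written anywhere.

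**Conclusion.** The concern holds. The NEQ formula in SAP 7.4.2 is wrong as written for the endpoint that both documents define. SAP 7.4.3 read alone introduces no volume effect; the error arises only if the displayed formula supplies its numerator. In that case an individual change can be off by a factor of two from volume alone, and an arm's geometric mean ratio by roughly 14% to 30% downward or 16% to 43% upward at the 95% limits, across the assumed SDs of 0.3 to 0.7 with independent volumes and no shift. The consequence is confined to NEQ. This should be fixed before programming, but it does not threaten the primary analysis.

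**What to change.** In SAP 7.4.2, delete the volume term and define NEQ as a concentration: either the molar sum in µmol/L, or the molar sum × 162.2 / 1000 in mg/L. Then divide by the creatinine concentration of the same spot urine as SAP 7.4.3 states, and name the reporting unit (mg/g creatinine or its molar equivalent) in 7.4.3 and 12.5.5.

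In the same edit, state the division by 1000 that takes the listed conversion factors from nmol/L to the µmol/L the formula needs. The section requires µmol/L but does not write that step.

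The cost is one line of SAP text and one line of code for the volume term, plus the unit clarifications. No new data are needed.
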